### Methodologies for FMT

Initially, patients identified their own donors selected from family or friends. Subsequently, some institutions offered the option of an anonymous donor(s). This shifts the burden of donor identification from the patient, creates a pool of tested healthy donors with a track record of cure, and also avoids donors with shared genetic or environmental susceptibilities to the recipient. An approach of using highly filtered human microbiota mixed with a cryoprotectant and then frozen for storage at  $-80^{\circ}\text{C}$  until required for use. This processing removes the fecal smell and reduces the volume of the filtrate. Use of such a

standardized, purified tissue has been shown to have equivalent clinical efficacy in treatment of C difficle infections.

Multiple routes of administration has been tried in FMT including naso-duodenal, transcolonoscopic, or enema based. A systematic review of FMT for C difficle suggested a lower success rate for upper gut administration (76 %), as compared with colonoscopy (89 %) and enema (95 %) administration.

A recent analysis had similar findings, with a trend toward higher CDI resolution rates with lower GI, rather than upper GI, administration (91 % vs. 82 %) although no head-to-head comparison has yet been performed – however, in liver diseases, the routes are not defined, but duodeno-jejunal region has been shown to have maximal dysbiosis.

### **3. AIMS AND OBJECTIVES**

#### **Research question**

Does FMT improve liver functions, prevent complications, reduce levels of pro-inflammatory cytokines and lead to an improvement in prognostic scores (CTP, MELD, MELD Na) and short-term survival in patients with DC?

#### **Study Hypothesis:**

In patients with DC, FMT may improve liver functions, prevent complications, reduce levels of pro-inflammatory cytokines and lead to an improvement in prognostic scores (CTP, MELD, MELD Na) and 180-day survival.

**Aim:**

To determine the role of FMT in improving liver function, prognostic scores, and short term mortality and reducing complications in patients with DC

**Objectives:**

**Primary Objective:** To assess the difference in 180-day mortality between the FMT group and the SOC group.

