#### **4. METHODOLOGY**

**Study design:** This will be an institute based prospective pilot study carried out in Postgraduate Institute of Medical Education and Research, Chandigarh from July 2018 to June 2020.

**Study period:** 15 months (from August 2018 to November 2019)

**Recruitment Period:** 10 months (August 2018 to May 2019)

**Sample Size:** 20 consecutive patients satisfying the selection criteria in each arm

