### **Randomization of patients**

Patients with decompensated cirrhosis who will be enrolled in the study after satisfying the selection criteria will be randomized into two groups 1:1 ratio using a random number generator

**Group 1(Experimental Arm):** Patients with decompensated cirrhosis who will receive Fecal MicrobiotaTransplantation via nasojejunal tube as well as traditional treatment for decompensated cirrhosis.

**Group 1(Standard of Care Arm):** Patients with decompensated cirrhosis who will receive standard medical treatment for decompensated cirrhosis.

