### **Follow Up post FMT**

Follow up of patients will be done at 7, 30, 90 and 180 days post FMT. During follow up patients will be evaluated for clinical parameters, routine biochemical monitoring and inflammatory markers for determining status of disease status.

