## **4. STATISTICAL ANALYSIS**

The results will be expressed as mean  $\pm$  standard deviation (SD) or median with range. Comparisons between groups will be performed using student's t-test or the Mann–Whitney U test. For categorical data chi-square test or Fisher's exact test will be applied. A value of  $P < 0.05$  will be taken as significant. The results will be analyzed at baseline and at day 7, 30 and 90 of the study. The in hospital survival curves will be made by the Kaplan-Meier method and compared with the log-rank test. All statistical tests will be done by Microsoft Excel and SSPSS Software version 18.

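### No effect estimate or confidence interval is planned for the primary outcome, 180-day mortality, and at 20 per arm a significance test alone says little

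*Combined protocol and SAP*

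**What the plan says.** The Objectives section sets the primary objective: "To assess the difference in 180-day mortality between the FMT group and the SOC group". The Methodology section calls the trial an "institute based prospective pilot study" and fixes the size at "20 consecutive patients satisfying the selection criteria in each arm", with no power, target effect or expected mortality. Patients are "randomized into two groups 1:1 ratio using a random number generator".

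The Statistical Analysis section is the only analysis plan in the protocol text. For a binary outcome it says "For categorical data chi-square test or Fisher's exact test will be applied", with no rule for choosing between them, and sets significance at P<0.05. For survival it says "The in hospital survival curves will be made by the Kaplan-Meier method and compared with the log-rank test". On timing it says "The results will be analyzed at baseline and at day 7, 30 and 90 of the study", whereas the follow-up section says "Follow up of patients will be done at 7, 30, 90 and 180 days post FMT". The summaries it names are mean with SD, or median with range. It mentions no risk difference, risk ratio, hazard ratio or confidence interval for any outcome.

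**The concern.** The objective asks for a difference, that is, a quantity. Nothing in the analysis section produces that quantity or shows how precisely it is known. What it does produce for mortality is a P value, plus curves whose in-hospital label and day-90 horizon do not match a 180-day outcome in a trial that also recruits outpatients.

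With 40 patients and a binary endpoint, a P value is a poor summary. A result above 0.05 could arise from no effect, a large benefit or a sizeable harm, and the P value does not tell these apart. A pilot is useful to a later trial mainly through its estimate and the width of the interval around it, and the plan specifies neither.

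**Working it through.** **Inputs from the protocol.** n = 20 per arm (Methodology); 1:1 allocation (Randomization); significance at P<0.05, and chi-square or Fisher for categorical data (Statistical Analysis).

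**Assumptions.** Tests are two-sided, since sidedness is not stated. SOC 180-day mortality is not given, so 10% to 40% is shown. All 40 patients have a known day-180 status. The stated 20 per arm cannot be reproduced because the protocol gives nothing to derive it from.

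**Step 1. Smallest significant result when FMT has no deaths.** Let k be the number of SOC deaths. By symmetry of the arms, the two-sided Fisher P is 2 × C(20,k) / C(40,k).
- k = 4: 2 × 4,845 / 91,390 = 0.106
- k = 5: 2 × 15,504 / 658,008 = 0.047

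Uncorrected chi-square is N(ad − bc)² divided by the product of the four margins.
- k = 3: 40 × (3 × 20)² / (20 × 20 × 3 × 37) = 3.24, P = 0.072
- k = 4: 40 × (4 × 20)² / (20 × 20 × 4 × 36) = 4.44, P = 0.035

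So Fisher needs at least 5/20 SOC deaths and uncorrected chi-square at least 4/20. A log-rank test without censoring behaves like the latter (k = 4: P = 0.037). Yates-corrected chi-square is stricter than Fisher (k = 5: P = 0.056; k = 6: P = 0.027). If FMT has 1, 2 or 3 deaths, the SOC deaths needed rise to 7, 9 or 10 (Fisher), or 6, 8 or 9 (uncorrected chi-square).

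**Step 2. Chance of missing P<0.05 even if FMT prevents every death.** This is P(X ≤ 4) for Fisher and P(X ≤ 3) for uncorrected chi-square, with X ~ Binomial(20, SOC mortality).

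| Assumed SOC mortality | Fisher | Uncorrected chi-square |
|---|---|---|
| 10% | 96% | 87% |
| 20% | 63% | 41% |
| 30% | 24% | 11% |
| 40% | 5% | 2% |

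**Step 3. Power if FMT halves mortality.** Sum the product of the two binomial probabilities over all 21 × 21 outcome tables with P<0.05.

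| SOC v FMT | Fisher | Uncorrected chi-square |
|---|---|---|
| 20% v 10% | 7% | 14% |
| 30% v 15% | 12% | 20% |
| 40% v 20% | 19% | 29% |

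**Step 4. What an interval would add.** Take 2 FMT deaths and 6 SOC deaths. The difference is 2/20 − 6/20 = −20 points, with Fisher P = 0.24. The Wilson 95% limits are 0.028 to 0.301 for 2/20 and 0.145 to 0.519 for 6/20. Newcombe's interval combines them:
- lower: −0.20 − √[(0.100 − 0.028)² + (0.519 − 0.300)²] = −0.43
- upper: −0.20 + √[(0.301 − 0.100)² + (0.300 − 0.145)²] = +0.05

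So a result reported only as not significant is compatible with anything from a 43-point reduction to a 5-point increase. Equal deaths, 4 v 4, give P = 1 and an interval of −25 to +25 points.

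**Step 5. Is the 180-day comparison scheduled?** Follow-up includes day 180, so the data should exist. The analysis section's list ends at day 90, and so does the list of SOC follow-up days under Pre FMT. The primary time point therefore has no stated analysis.

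**The case against.** **The size of the problem depends on choices the protocol leaves open.** This stands. A reader might infer that significance is usually out of reach at this sample size, even for a perfect treatment. The documents do not support that as a general statement. They give no SOC mortality and do not assign Fisher's test to mortality. With uncorrected chi-square, 0 v 4 is significant, and at 40% SOC mortality the failure rate in the best case is only 5% or 2%. However, preventing every death is an extreme case. With a halving of mortality, power stays below 30% under both tests at every rate in Step 3.

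**The plan gives more than a P value.** This stands in part. Kaplan-Meier curves by arm would be drawn, death counts would normally be reported, and an interval could be computed from those counts later. So the loss is in pre-specification and presentation rather than in data. But the curves are labelled in-hospital, and neither they nor the log-rank test supply a 180-day difference with its uncertainty.

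**The harm is a forecast.** This also stands in part. A reader might infer that the investigators intend to report a non-significant result as no effect. Nothing in the protocol says so. The introduction speaks of feasibility and safety, the design is labelled a pilot, and the ethics annexure commits to accuracy for positive and negative results alike. None of this removes mortality as the primary objective or supplies an estimate of it, and the pilot label makes the missing interval matter more.

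**Newcombe's method is one choice among several.** Agreed. Any interval suited to small samples would do, and how the P value ranks beside it is a matter of preference.

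**Conclusion.** The concern holds in conditional form. That no between-group estimate or interval is planned for 180-day mortality, and that no day-180 analysis time is listed, follows from the text and needs no assumption. How little the test alone can show does rest on assumptions: two-sided testing, complete day-180 status and an assumed SOC mortality. Best-case failure is common at 20% SOC mortality or below, at 41% or more under either test, and becomes rare by 40%. The low power for a halving of mortality holds across the whole assumed range. This should be changed before analysis. It does not make the trial unsound or call for a larger sample.

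**What to change.** In Statistical Analysis, add day 180 to the analysis times and extend the survival curves beyond the hospital stay to day 180. Define the primary result as the 180-day risk difference (FMT minus SOC) with a 95% interval suited to small samples, such as Newcombe's, reported alongside the P value. If patients are lost before day 180, the Kaplan-Meier difference at day 180 with its interval is the alternative. Name which categorical test applies to mortality. Bring the SOC follow-up days under Pre FMT into line with the 180-day schedule.

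Beside the sample size in Methodology, state that this pilot estimates mortality and that P≥0.05 will not be reported as absence of a difference.

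The cost is a few sentences and one extra line of output, with no added patients or data. The downside is a more modest stated conclusion, since the interval will usually be wide (about 50 points in the examples above).

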**Secondary Objective**

1. To assess and compare the changes in liver function in both groups based upon
  - CTP score at 28 days, 90 days and 180 days
  - MELD Score at 28 days, 90 days and 180 days
  - MELD Na Score at 28 days, 90 days and 180 days
2. To compare the complications in both groups in a follow-up period of 180 days
3. Changes in inflammatory markers (IL-1b, IL-6) in both groups at 28 days

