## **Study Protocol:**

**Title:** Single Session of Fecal Microbiota Transplantation in Decompensated Cirrhosis: An open-label randomized control trial

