### **The FMT Procedure**

In the Fecal Microbiota Transplantation procedure 100 ml volume of strained and filtered stool will be delivered through a nasojejunal tube. The recipient patient will be kept nil per oral for at least 4 hours prior to the stool instillation. 100 mL of freshly prepared stool suspension will be given. IV antibiotics will be continued as per treating physician's decision in the event of active sepsis based on culture and sensitivity. The duodenal tube will be flushed with normal saline (30mL) after the stool instillation. The patient will be allowed to consume liquid diet two hours after the procedure. All patients will continue on salt restriction, diuretics, and 1.5g/kg per day of plant and egg based protein and weight based recommended calorie intake as prescribed by the dietician. Intravenous albumin will be continued as indicated during hospitalized period. While rifaximin and other non-absorbable antibiotics will be withheld, disaccharides will be permitted to have 2-3 soft stools per day.

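### CTP, which includes two bedside grades, ranks equally with MELD and MELD-Na as a measure of liver function in an open-label trial, and the plan cannot separate a grading shift from a change in the liver

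*Combined protocol and SAP*

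**What the plan says.** The title describes the study as "An open-label randomized control trial". The first item under Secondary Objective is "To assess and compare the changes in liver function in both groups based upon" three scores, listed in parallel: "CTP score at 28 days, 90 days and 180 days", "MELD Score at 28 days, 90 days and 180 days" and "MELD Na Score at 28 days, 90 days and 180 days". None is named as the lead. The Research question and Study Hypothesis also list the three together as prognostic scores.

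On assessment, Follow Up post FMT says: "During follow up patients will be evaluated for clinical parameters, routine biochemical monitoring and inflammatory markers". It does not say who grades ascites or encephalopathy, or by what criteria. No section describes a masked assessor or adjudication.

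The Statistical Analysis section gives a t-test or Mann-Whitney test at P < 0.05. It contains no ranking of the scores, no analysis of CTP by component, and no statement on how discordant scores would be interpreted.

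The Primary Objective is "To assess the difference in 180-day mortality between the FMT group and the SOC group", an outcome that grading cannot move.

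**The concern.** The three scores are not equally exposed to an open-label design. By the standard definitions (the protocol does not define the scores), CTP adds five items, each scored 1 to 3. Bilirubin, albumin and INR come from the laboratory. Ascites and encephalopathy are judged at the bedside. MELD and MELD-Na have no bedside-graded item.

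A clinician who knows that a patient received FMT may grade borderline ascites or encephalopathy a step more favourably, without intending to. CTP would then fall with no change in the liver. Because CTP stands level with the other two scores, such a difference could be reported as improved liver function. Adjusting for multiple tests would not cure this: it limits chance findings, whereas a grading shift is systematic.

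Liver function comes first in the research question, the hypothesis and the aim. With 20 patients per arm in a self-described pilot, the secondary scores may carry much of the interpretation.

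**Working it through.** The plan gives no power, effect size or standard deviation for CTP, so there is no figure of its own to reproduce. The calculation below only shows how sensitive a CTP comparison would be to grading.

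**Inputs from the document**
- n = 20 per arm (Methodology, Sample Size)
- 1:1 allocation (Randomization of patients)
- Significance at P < 0.05 (Statistical Analysis); two-sided is assumed, since the plan does not say

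**Assumed inputs**
- Standard deviation of the analysed CTP value: 1.25, 1.5 or 2.0 points
- Mean between-arm grading shift: 0.25 or 0.5 points. A shift of 0.5 means half the FMT patients are graded one step lower on one item (0.5 × 1); 0.25 means a quarter are
- No true effect on the liver

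**Share of CTP open to grading.** Five items scored 1-3 give totals from 5 to 15, a range of 10. The two graded items span 2 × (3 − 1) = 4 of those 10 points, or 40%. This is the nominal maximum.

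**Formula.** SE = SD × √(2/20). Noncentrality = shift / SE. The rejection rate is the probability that a noncentral t with 38 degrees of freedom falls beyond ±2.024.

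| SD | SE | Rejection rate, shift 0.25 (noncentrality) | Rejection rate, shift 0.5 (noncentrality) |
|---|---|---|---|
| 1.25 | 0.395 | 0.095 (0.632) | 0.234 (1.265) |
| 1.5 | 0.474 | 0.081 (0.527) | 0.177 (1.054) |
| 2.0 | 0.632 | 0.067 (0.395) | 0.120 (0.791) |

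The nominal 5% becomes about 7-10% for a quarter-point shift and 12-23% for a half-point shift. Most rejections favour FMT. At SD 1.5 and shift 0.5, for example, 0.176 of the 0.177 lies in that direction, where the nominal rate is 2.5%.

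**Which end is more plausible.** Exclusion Criteria item 4 removes patients with overt encephalopathy in the previous 14 days, and Inclusion Criteria item 3 requires capacity to consent. Most patients should therefore enter at or near the lowest encephalopathy grade, which cannot be graded lower. Later episodes could still be under-graded, but most of any shift would have to come from ascites. That makes the 40% span generous and favours the lower half of the table.

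**The case against.** **The unblinded grading is inferred.** No section names the CTP assessor. The inference is reasonable for an open-label trial that describes no masked assessment, but it remains an inference. The plan also contains no success rule for liver function, so it does not say that CTP alone would suffice; it only leaves that open.

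**The size is hypothetical.** The standard deviation, the shift and the proportion shifted are all assumed, and the objective concerns changes, whose standard deviation may differ from that of the score itself. The plan also allows the Mann-Whitney test: a simulation of rounded scores with half the FMT arm shifted gave about 11-20%, slightly below the t-test's 12-23%. This stands, and the figures show sensitivity only.

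**MELD and MELD-Na are not immune to an open-label design.** A reader might infer that they are. They avoid bedside grading but not co-treatment chosen by physicians who know the arm. The FMT Procedure and Management post FMT sections mention diuretics, intravenous albumin, vasoactive agents and dialysis, which plausibly move creatinine and sodium. Intravenous albumin can likewise move CTP's albumin item. This stands and must be acknowledged.

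**A CTP difference without a matching MELD difference is not thereby an artefact.** A reader might want a rule that sets such differences aside. That would be unsound. Albumin is in CTP but not in MELD or MELD-Na, so a laboratory gain would be discarded. Real change in ascites or encephalopathy, which the Introduction's hypothesis targets, would be dismissed too. With 20 per arm, a non-significant MELD difference is weak evidence against a CTP one.

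**The consequence is limited.** CTP is one of three scores under one secondary objective in a pilot, and MELD and MELD-Na at the same visits would let readers see discordance. This limits the severity. It does not remove the gap, since the plan provides no component analysis to explain any discordance.

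**Conclusion.** The point holds as an inexpensive improvement to a secondary objective. The open-label design, the equal standing of the three scores and the absence of any masked grading or component analysis are all in the text. That the graders know the arm is inferred, and the make-up of the scores rests on their standard definitions.

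Under the assumed SDs of 1.25-2.0, a mean grading shift of 0.25-0.5 points raises the false-positive rate of a CTP t-test from 5% to about 7-23%, with the lower end more plausible. Nothing in the documents shows that such a shift will occur, or how large it would be. The primary mortality comparison is not touched.

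A related inconsistency bears on the encephalopathy item. Pre FMT has lactulose and rifaximin continued in all patients where indicated. The FMT Procedure states "While rifaximin and other non-absorbable antibiotics will be withheld, disaccharides will be permitted to have 2-3 soft stools per day". Management post FMT treats encephalopathy with lactulose and rifaximin. These statements must be reconciled. Until they are, an arm difference in encephalopathy grade cannot be cleanly attributed to the liver, whoever does the grading.

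**What to change.** Under Secondary Objective and in Statistical Analysis:

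1. Name MELD or MELD-Na as the lead measure of liver function, with CTP supportive.
2. Analyse CTP's laboratory items (bilirubin, albumin, INR) separately from its ascites and encephalopathy grades, by arm and visit.
3. State that a CTP difference will be interpreted by whether the laboratory items contribute to it. Do not adopt a rule that disregards every CTP difference not matched by MELD.
4. Acknowledge that MELD and MELD-Na avoid bedside grading but not the effect of unblinded co-treatment.
5. Reconcile the three rifaximin statements in Pre FMT, The FMT Procedure and Management post FMT.

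Items 1 to 4 use data the plan already needs in order to compute CTP. They require no extra patient, visit, test or assessor, and leave the sample size unchanged. The cost is protocol wording and one extra table. The downside is small: CTP alone no longer carries the liver-function claim. The change does not remove any grading bias, but it lets the report show whether a CTP difference rests on graded items alone.

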#### **4. METHODOLOGY**

**Study design:** This will be an institute based prospective pilot study carried out in Postgraduate Institute of Medical Education and Research, Chandigarh from July 2018 to June 2020.

**Study period:** 15 months (from August 2018 to November 2019)

**Recruitment Period:** 10 months (August 2018 to May 2019)

**Sample Size:** 20 consecutive patients satisfying the selection criteria in each arm

## **Study population**

All patients with decompensated cirrhosis who will be admitted to the Department of Hepatology in Medical Ward Unit or Liver ICU of Postgraduate Institute of Medical Education and Research (PGIMER) or will be attending the outpatient department of PGIMER during the period from August 2018 till May 2019 will be screened for eligibility for enrollment after ethical approval from the institute ethics committee. An informed consent will be taken from all the participants. Those patients who satisfy the inclusion and exclusion criteria and provide a valid informed consent will be enrolled in the study.

